# 8.4. Labeling, Packaging, Infusion Supplies, and Storage and Handling

# 8.4.1. Labeling

Labels containing study information and pack identification are applied to the investigational product(s) container.

All investigational product is labeled with a minimum of the following: protocol number, dosage form (including product name and quantity in pack), route of administration, directions for use, storage conditions, batch number and/or packaging reference, the statements required per local regulations (eg, "For clinical trial use only"), and name and address of the sponsor.

Space is allocated on the label so that the site representative can record a unique subject identifier and date dispensed by the site to the subject.

Additional labels may, on a case-by-case basis, be applied to the investigational product in order to satisfy national, local, or institutional requirements but must not do any of the following: contradict the clinical study label, obscure the clinical study label, identify the study subject by name.

Additional labels may not be added without the sponsor's prior full agreement.

## 8.4.2. Packaging

Investigational product is supplied in 20-mL glass vials. Please refer to the pharmacy manual for details.

Changes to sponsor-supplied packaging prior to dosing may not occur without full agreement, in advance, by the sponsor.

## 8.4.3. Infusion Supplies

The sponsor will supply syringes, vial adapters, infusion sets, and ambulatory syringe infusion pumps, as required. Refer to the pharmacy manual for further details.

## 8.4.4. Storage and Handling

The investigational product should be stored refrigerated at 2-8 °C, both at home and in the clinic. Temperature monitoring is required at the investigator site (or documented storage location) to ensure that the investigational product is maintained within an established temperature range.

The investigator or appropriately qualified site staff will be responsible for the following:

 ensuring that the investigational product is stored in a secure, limited-access location at the site

- limited responsibility may be delegated to the pharmacy or member of the study team, but this delegation must be documented
- ensuring that the temperature is monitored throughout the duration of the study and that records are maintained

A pharmacist or appropriately qualified designated person will be responsible for the following:

- storing the investigational product appropriately
- dispensing the vials of investigational product to the subject
- entering the unique subject identifier on the investigational product bottle/carton labels as they are distributed

When the subject receives the investigational product from the site, it should be transported in a sponsor-approved bag or box containing previously temperature-conditioned cold plates to ensure that the storage temperature (2-8 °C) is maintained. Temperature monitoring will not be required during transport or at the subject's residence, but a log will be kept for every infusion to ensure that all investigational product was kept refrigerated.

With sponsor prior approval, investigational product and/or ancillary supplies may be shipped from the study site to a subject's designated location. Such shipments will only be implemented at sites where this activity is approved by the IRB/EC and health authority (if required). Subject consent will be required prior to any subject information being provided to a courier. The responsibility to return both empty vials and any unused investigational product shall remain unchanged.

## 8.5. Measures to Minimize Bias: Study Treatment Assignment

Randomization will occur through the interactive response technology system.

# 8.5.1. Method of Study Treatment Assignment

All subjects who meet all the inclusion criteria and none of the exclusion criteria will be enrolled in the study, until such time that up to 12 subjects have been enrolled in the study. Subjects will then be randomized through the interactive response technology system to either Group 1 (pegcetacoplan) or Group 2 (control). Following completion of the main period, all subjects will enter the follow-up period unless they enter the sponsor-planned long-term extension protocol.

# 8.6. Investigational Product Accountability

Investigators will be provided with sufficient amounts of the investigational product to carry out this protocol for the agreed number of subjects. The investigator or designee will acknowledge receipt of the investigational product, documenting shipment content and condition. Accurate records of all investigational product dispensed, used, returned, and/or destroyed must be maintained. The investigator is responsible for ensuring the retrieval of all returnable study supplies from subjects.

At the conclusion of the study, any unused investigational product will either be destroyed at the investigator site or be returned to the sponsor or designee for destruction, and destruction will be documented appropriately. If no supplies remain, this fact will be documented appropriately.

# 8.7. Subject Compliance

Subjects must be instructed to bring their empty/unused investigational product packaging to every visit. The pharmacist/nominated person will record details on the drug accountability form.

## 8.8. Prior and Concomitant Medications and Procedures

All medications administered and procedures performed within 12 weeks of screening will be collected as prior medications and procedures. Medications administered and procedures performed from the time of informed consent through the end-of-study visit are regarded as concomitant and will be documented. Use of rituximab, belimumab, eculizumab, and ravulizumab during the study (and/or within 24 weeks prior to the first dose of pegcetacoplan) must be discussed with the sponsor for consideration and approval.

Subjects should be on stable doses of all medications relevant to their renal disease for at least 4 weeks prior to the screening renal allograft biopsy until the end of the study. During the study, including the screening period, changes to the baseline treatment regimens (including medications, dietary restrictions, and lifestyle modifications) should be minimized to the extent possible and made only when required for the well-being of the subject. However, in the setting of an acute crescentic glomerulonephritis at the time of study entry, steroid treatment may be initiated along with, or around the same time as, pegcetacoplan treatment, if deemed necessary by the investigator.

If the subject is in a post-transplant time frame in which immunosuppression or other transplant-related medication adjustments are anticipated, these adjustments should still occur, adhering to the center's standard protocol for post-transplant care. For all subjects, the plan for post-transplant immunosuppression for the duration of the study should be documented prior to randomization. Any deviation during the study from the prespecified plan should be documented with a justification for the change. Subjects with evidence of rejection on the screening biopsy that requires treatment will need to undergo their antirejection treatment, and then can be reconsidered for pegcetacoplan dosing, but will need to meet all other study eligibility criteria, including a screening biopsy that is within the designated assessment window, to serve as the baseline (refer to Section 9.1.3 for further details). Subjects with evidence of subclinical rejection on the screening biopsy may proceed with pegcetacoplan treatment, at the discretion of the investigator, provided no treatment is initiated for the rejection.

## 8.8.1. Empiric Antibiotic Treatment for Possible Infection

Body temperature, vital signs, and relevant blood parameters will be monitored regularly throughout the study to assess for signs of infection. The investigator should be contacted immediately in the event of a suspected infection for guidance on appropriate action to be taken. Action to be taken may include empiric administration of a broad-spectrum antibiotic to cover possible serious infections, such as meningococcus.

#### 9. STUDY PROCEDURES

Table 1 outlines the timing of procedures and assessments to be performed throughout Part A of the study, once written informed consent has been obtained from the subject. Section 10.13 specifies laboratory assessment samples to be obtained. The schedule of visit dates should be established, either prior to or at the time of screening to allow subjects an opportunity to assess whether there are likely to be significant conflicts with other activities or planned absences. To the extent possible, subjects will be expected to adhere to the visit schedule, and any rescheduling of visits must be agreed, in advance, with the investigator and sponsor.

The investigator may, at his/her discretion, arrange for a subject to have an unscheduled assessment, especially in the case of AEs that require follow-up or are considered by the investigator to be possibly related to the use of study drug. The unscheduled visit page in the eCRF must be completed.

Study discontinuation procedures are described in Section 7.2.1.

Details regarding participation in Part B, the long-term extension, are provided in the appendices (Section 15).

Table 1: Schedule of Activities for Part A

Study Period	per	ening iod						Main period  Noncontrolled portion									Follow-up perio		s)
	8 we	eks) bjects A		Contr	olled p	ortion											All subjects not entering Part B		
Study Week	−8 to −4	-2	1	2	4	8	12	14 B	16	20	24	30	36	42	48	52	54	56	60 Exit
Study Day	–56 to –28	-14	1	14	28	56	84	98	112	140	168	210	252	294	336	364	378	392	420
Study Visit	1	2	3	4	5	6	7	8	9	10	11	12	13	14	15	16	17	18	19
Visit window (± days)	N/.	A C	0	3	3	7	7	7	7	7	7	7	7	7	7	7	3	3	7
Informed consent	X																		
Demographics	X																		
Medical history	X																		
Inclusion/exclusion D	X	X	X																
Vaccination E		X				X													
Concomitant medications	х	X	X	X	X	X	X	X	x	Х	Х	X	X	X	X	X	X	X	X
Physical examination F	X	X	X	X	X	X	X	X	X	X	X	X	X	X	X	X	X	X	X
12-lead ECG	X		X	X	X	x	x	X	X	x	x	X	X	X	X	x	X	X	X
Renal biopsy G	2	ζ.		X X															
Randomization			X																
Pegcetacoplan administration B				Group 1 only				All subjects											
Infusion site/pump safety assessment H				Group 1 only				All subjects											

Table 1: Schedule of Activities for Part A

Study Period	per (up	o to		Main period									(8	Follow-up period (8 weeks)					
		eks) bjects A		Contr	olled p	ortion				N	oncon	trolled	portio	n			All subjects not entering Part B		
Study Week	−8 to −4	-2	1	2	4	8	12	14 B	16	20	24	30	36	42	48	52	54	56	60 Exit
Study Day	–56 to –28	-14	1	14	28	56	84	98	112	140	168	210	252	294	336	364	378	392	420
Study Visit	1	2	3	4	5	6	7	8	9	10	11	12	13	14	15	16	17	18	19
Visit window (± days)	N/.	A C	0	3	3	7	7	7	7	7	7	7	7	7	7	7	3	3	7
Vital sign measurements I	x	x	X	x	X	X	х	х	x	X	X	х	х	X	X	X	X	Х	х
Urine samples (below)																			
24-hour urine collection J	2	ĸ					х				X				X				Х
Triplicate first- morning spot urine K		х	X L								Sec T	able 2							
In-clinic (random) spot urine	x	x	х	х	х	x	х	х	х	X	x	х	х	х	X	X	х	х	х
Urinalysis (microscopic & dipstick) M	x	x	х	х	х	х	х	х	х	х	х	х	х	х	х	х	х	х	x

Table 1: Schedule of Activities for Part A

Study Period		ening iod to		Main period										(8	Follow-up period (8 weeks)				
		eks) ojects A		Controlled portion Noncontrolled portion							All subjects not entering Part B								
Study Week	−8 to −4	-2	1	2	4	8	12	14 B	16	20	24	30	36	42	48	52	54	56	60 Exit
Study Day	–56 to –28	-14	1	14	28	56	84	98	112	140	168	210	252	294	336	364	378	392	420
Study Visit	1	2	3	4	5	6	7	8	9	10	11	12	13	14	15	16	17	18	19
Visit window (± days)	N/.	A C	0	3	3	7	7	7	7	7	7	7	7	7	7	7	3	3	7
Blood samples (below)																			
Hematology M & chemistry M	х	х	х	х	х	X	х	х	х	х	X	X	х	X	X	Х	х	X	х
PK sample			X N	X N	XN	$\mathbf{X}^{\mathbf{N}}$	X N	х	х	х	x	X	х	X	X	х	X	X	х
ADA assays 			XN	XN	XN	XN			Х		X		Х			X	X		Х
Complement profile M			X	X	X	X	X	X	х	х	X	X	х	X	X	X	Х	X	Х
C3 nephritic factor	x		x																
eGFR P,Q	Х	X	х	х	X	Х	X	X	Х	X	X	X	Х	X	X	X	Х	Х	Х
Pregnancy (β-HCG)	X															X			

Table 1: Schedule of Activities for Part A

Study Period	Scree per (up			Main period							(8	Follow-up period (8 weeks)							
		eks) ojects A	Controlled portion				Noncontrolled portion									All subjects not entering Part B			
Study Week	−8 to −4	-2	1	2	4	8	12	14 B	16	20	24	30	36	42	48	52	54	56	60 Exit
Study Day	–56 to –28	-14	1	14	28	56	84	98	112	140	168	210	252	294	336	364	378	392	420
Study Visit	1	2	3	4	5	6	7	8	9	10	11	12	13	14	15	16	17	18	19
Visit window (± days)	N/.	A C	0	3	3	7	7	7	7	7	7	7	7	7	7	7	3	3	7
Urine pregnancy test		X	X	X	X	X	X	X	X	X	X	X	X	X	X	X	X	X	X
FSH, HIV, HCV, HBsAg, HBcAb R	х																		
AEs	Х	X	х	Х	Х	Х	X	X	Х	Х	Х	X	Х	X	X	X	X	X	X
Post-transplant immunosuppression plan documentation		x																	
Ophthalmologic evaluation (optional) S		XS													XS				

Abbreviations: ADA = antidrug antibodies; AE = adverse events;  $\beta$ -HCG =  $\beta$ -human chorionic gonadotropin; CDC = Centers for Disease Control and Prevention;

NOTE: When multiple assessments/procedures occur at the same time, order should be: vital signs, ECGs, blood collection/sampling, pegcetacoplan dosing.

CKD-EPI = Chronic Kidney Disease-Epidemiology Collaboration; ECG = electrocardiogram; eGFR = estimated glomerular filtration rate;

FSH = follicle-stimulating hormone; GFR = glomerular filtration rate; HBcAb = hepatitis B core antibody; HBsAg = hepatitis B surface antigen;

HCV = hepatitis C; N/A = not applicable; PK = pharmacokinetic(s); RBC = red blood cell; SC = subcutaneous;

SD-OCT = spectral domain optical coherence tomography.

A. Subjects who meet the medical history requirements will enter the screening period at Visit 1 and return for Visit 2, but all Visit 2 assessments need not occur in a single visit and Visit 2 can be split into multiple visits (eg, 2a, 2b).

- B. Subjects will self-administer SC pegcetacoplan after receiving appropriate training and sign-off by a research nurse or other personnel in their first treatment week. During site visits subjects will self-administer pegcetacoplan at the site, with the exception of the very first dose. Group 2 subjects will be trained on self-administration of pegcetacoplan and receive their supply of pegcetacoplan at the next scheduled clinic visit (Visit 7 or 8) following their biopsies.
- C. Visit 2 must occur at least 7 days after Visit 1 and at least 14 days prior to the Day 1 dosing date; the vaccinations and biopsy can occur any time after confirmation of eligibility based on Visit 1 data.
- D. Specific inclusion/exclusion criteria will be measured during screening, and some of them require confirmation prior to any activities of Day 1. See the inclusion/exclusion criteria in Section 7 for further detail.
- E. Vaccinations against N. meningitidis, S. pneumoniae, and H. influenzae are mandatory, unless documented evidence exists that subjects have received all recommended vaccines or are nonresponders to vaccination. Any required vaccines should be administered during screening (Day -14), and any required boosters should be administered at Visit 6 (Day 56), unless an alternative vaccination schedule has been agreed with the medical monitor, as described in Section 9.1.4. Subjects who withdraw from the study prior to a scheduled vaccine booster, as recommended by the current Advisory Committee on Immunization Practices adult immunization schedule, will be offered the opportunity to return to the site to receive the booster. Vaccination serum samples (for antibody titer) will be collected prior to subject receiving vaccinations on that study visit.
- F. Full physical examination will only be performed at Study Weeks -4, 1, and 52. Brief physical examinations will be conducted at all other clinic visits, as noted. A symptom-driven physical examination may be performed at other times, at the investigator's discretion. Body height (cm) will be measured during screening only and weight (kg) will be measured throughout study, during brief and full physical examinations. Edema should be assessed at every visit.
- G. Week 12 biopsy must occur at a time point between Weeks 12 and 14, inclusive; Group 2 subjects cannot begin pegcetacoplan administration until after the biopsy occurs. Week 52 biopsy must occur at a time point between Weeks 48 and 52, inclusive, but after completion of the 24-hour urine collection scheduled for Week 48.
- H. Between site visits, subjects will be instructed to report any infusion site reaction to the study staff. Pump use safety assessment will be performed by licensed health care professional (ie, investigator or nurse) within 30 minutes following study drug administration at all clinic visits and during at-home qualification. See Manual of Procedures for more details.
- I. When pegcetacoplan is administered at the study site, vital signs will be measured within 2 hours prior to infusion, before venipuncture and ECG. Following the first infusion, vital signs will be measured again at 30 minutes (±5 minutes) after dosing. For subjects in Group 2, vital signs will be measured once at each visit during the controlled period. For all evaluations, blood pressure and heart rate should be evaluated after the subject has been resting in a seated, recumbent, or supine position for at least 5 minutes.
- J. The 24-hour urine collection requires collection of 24 hours of urine in a pooling container following the first urinary output on that day (first urinary output is discarded). The screening 24-hour urine collection should be done following Visit 1. Courier arrangements will be made by site personnel to pick up urine containers from subject's home. This collection should be done prior to the renal biopsy.
- K. Urine protein-to-creatinine ratio samples (first urinary output for the day) should be collected on 3 consecutive days, every 2 weeks, throughout the study. On weeks of scheduled clinic visits, samples will be brought with subject during the site visit. On weeks when no clinic visit is scheduled, courier service will be arranged for urine sample pickup and delivery to the site.
- L. The Day 1 triplicate first-morning urine samples should be collected before the first dose of pegcetacoplan (eg, Day -2, Day -1, and Day 1) and are required for randomization.
- M. See laboratory assessments (Table 3) for more details.
- N. During the controlled period, PK and ADA samples will be collected from subjects in Group 1 only.
- O. Subjects who discontinue dosing will need to have ADA samples collected at 6 and 12 weeks after the last treatment. Subjects who test positive for anti-pegcetacoplan peptide or anti-PEG antibodies at any time will be followed up with ADA samples being collected every 6 months until the antibody levels revert to baseline.

03 February 2022

- P. Measured GFR is an optional assessment which, if done, should performed at 2 time points: once on Day 1, or within 4 weeks before Day 1, and again at 1 time point between Week 48 and Week 52, inclusive. Measured GFR should only be done at sites where it is routinely performed, as per the site's standard protocol.
- Q. CKD-EPI creatinine equation; the CKD-EPI creatinine-cystatin C equation (if confirmation required).
- R. Serum FSH to be performed on women only (see laboratory manual for more details).
- S. Ophthalmologic evaluations are optional and will be performed at selected sites. If these evaluations are performed, subjects should have a baseline evaluation, including a basic ophthalmologic examination, SD-OCT, and color fundus photography, at an approved ophthalmologic clinical site at any time during the screening period. For those subjects with drusen prior to pegcetacoplan administration, a follow-up ophthalmologic evaluation, including a basic ophthalmologic examination, SD-OCT, and color fundus photography, should occur at a convenient time point between Week 42 and Week 52 of the study.

Table 2: First-Morning Urine Collection Schedule

				5	Screening a	nd main p	eriod, Wee	ks –2 to 24	1						
Study Week	-2	1	2	4	6	8	10	12	14	16	18	20	22	24	
Study Day	-14	1	14	28	42	56	70	84	98	112	126	140	154	168	
Study Visit	2	3	4	5		6		7	8	9		10 11			
Triplicate first- morning spot urine	x	х	х	х	х	х	x	х	х	х	х	x	х	х	
uPCR containers to be dispensed	3	3	3	6		6		3	3	6		6		9	
		Main period, Weeks 26 to 52													
Study Week	26	28	30	32	34	36	38	40	42	44	46	48	50	52	
Study Day	182	196	210	224	238	252	266	280	294	308	322	336	350	364	
Study Visit			12			13			14			15		16	
Triplicate first- morning spot urine	х	х	х	х	х	x	х	х	х	х	x	x	х	х	
uPCR containers to be dispensed			9			9			9			6		3	
					Follow	-up period	(Weeks 54	ta 60)							
Study Week		54				56			58				60		
Study Day		378	378 392						406				420		
Study Visit	17					18							19		
Triplicate first- morning spot urine	x				x				х			x			
uPCR containers to be dispensed	3				6								n/a		

Abbreviations: n/a = not applicable; uPCR = urine protein-to-creatinine ratio.

Note: Shaded columns indicate samples to be collected at home and brought to the clinic during visit weeks; unshaded columns indicate samples to be collected at home and picked up by courier during nonvisit weeks.

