# 10.17. Antidrug Antibody Assessment

Antidrug antibodies (ADA) include both anti-pegcetacoplan peptide and anti-PEG antibodies.

The proposed ADA sampling schedule was established to capture the ADA signal at baseline, along with any potential early onset and the dynamic profile (transient or persistent) of antibody formation.

Subjects who discontinue dosing will need to have ADA samples collected 6 and 12 weeks following their last treatment.

Samples that test positive will be characterized by assays that will determine antibody titer and measure neutralizing capacity. Any titer that is at least 4-fold greater than baseline is considered treatment boosted. Subjects who have a treatment-emergent or treatment-boosted antidrug antibody response at any time will be followed up with ADA samples being collected every 6 months until the antibody levels are considered to be negative. Antibody levels will be considered to be negative when they revert to baseline or any titer that is less than a 4-fold increase from the baseline titer.

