The number and percentage of subjects with pre-existing ADAs will be summarized by treatment group and overall in the subjects with a baseline sample result. In addition, the number and percentage of subjects with an ADA positive response, ADA negative response, and ADA inconclusive response as well as the type and kinetics of the positive ADA response will be summarized by treatment group and overall in the evaluable subjects. The subject summary table will include a summary by treatment group and overall for the ADA population parameters. The subject summary table will also include the number and percentage of subjects with a positive NAb result either pre- or post-dose in the subjects with at least one pre- or post-dose sample result.

Pre-existing ADA will be defined as follows: any subject with an ADA positive baseline sample from the total subjects with a baseline sample result.

Evaluable subjects will be defined as follows: a subject with at least one sample taken with a reportable result after first dosing during the treatment or follow-up period.

Evaluable subjects will be classified as follows for ADA response:

- ADA-Positive Subject – An evaluable subject with at least one pre-dose sample and one treatment-emergent or treatment-boosted ADA-positive sample at any time after dosing
- ADA-Negative Subject – An evaluable subject without a treatment-emergent or treatment-boosted ADA-positive sample during the treatment or follow-up period
- ADA-Inconclusive Subject – An evaluable subject who cannot be classified as either ADA-positive or ADA-negative (eg, assay drug tolerance issues, post-dose positive without a baseline sample, positive baseline and positive post-dose sample without a titer value, etc.)

ADA positive responses will be classified as follows:

- Treatment-Boosted ADA Response – An evaluable subject with a baseline ADA positive sample and a post-dose ADA positive sample that is $\geq 4x$ the baseline titer (eg, baseline titer of 10 vs. post-dose titer of 40)
- Treatment-Emergent ADA Response – An evaluable subject with a baseline ADA negative sample and an ADA positive sample after treatment, ADA developed *de novo*

The kinetics of ADA positive responses will be classified as follows:

- Transient ADA Response

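### As scheduled, Group 2 has no antidrug-antibody sample before its first dose, so its ADA incidence under SAP Section 10 is 0 whatever the data show (minor)

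*Protocol*

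**What the plan says.** **Sampling.** The ADA row of Protocol Table 1 is marked at Weeks 1, 2, 4 and 8, each with footnote N, and then at Weeks 16, 24, 36, 52, 54 and 60. Screening, Week 12 and Week 14 are blank. Footnote N reads: "During the controlled period, PK and ADA samples will be collected from subjects in Group 1 only".

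**First dose in Group 2.** Under footnote B, these subjects "receive their supply of pegcetacoplan at the next scheduled clinic visit (Visit 7 or 8) following their biopsies", that is, at Week 12 or Week 14.

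**Stated aim.** Protocol 10.17 says: "The proposed ADA sampling schedule was established to capture the ADA signal at baseline". It makes no exception for Group 2.

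**Classification in SAP Section 10.**
- An evaluable subject is "a subject with at least one sample taken with a reportable result after first dosing". No baseline is required.
- An ADA-positive subject is "An evaluable subject with at least one pre-dose sample and one treatment-emergent or treatment-boosted ADA-positive sample at any time after dosing".
- A treatment-emergent response is "An evaluable subject with a baseline ADA negative sample and an ADA positive sample after treatment". A treatment-boosted response needs a positive baseline sample and a post-dose titer at least 4 times that baseline.
- The examples of an inconclusive subject include "post-dose positive without a baseline sample".
- Pre-existing ADA is "any subject with an ADA positive baseline sample from the total subjects with a baseline sample result".
- Incidence is the count of treatment-emergent plus treatment-boosted subjects divided by all evaluable subjects. It is reported by group and overall.

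**The concern.** The numerator of ADA incidence needs a pre-dose sample and the denominator does not. A group that is never scheduled for a pre-dose sample can therefore add to the denominator but never to the numerator. A printed 0% for Group 2 would read as an observation when it is produced by the definitions, and the overall figure is pulled down with it.

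Four related items have the same cause:
- The pre-existing line for Group 2 has an empty denominator.
- Both parts of the prevalence numerator (ADA-positive and pre-existing) need a pre-dose sample.
- The SAP's ADA-negative class covers any evaluable subject without a treatment-emergent or treatment-boosted sample. Read literally, it also takes in a Group 2 subject who is positive after dosing, and so overlaps with the inconclusive class.
- Protocol 10.17 and footnote O stop extended ADA sampling by reference to baseline, which Group 2 would not have.

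Protocol 5.2.5 names the incidence of these antibodies, including treatment-emergent and treatment-boosted responses, as an endpoint. Protocol 12.7 asks for ADA results by treatment group.

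**Working it through.** **1. Check the reading of Table 1 against Table 4.** The ADA row has 19 visit columns. The marked main-period weeks are 1, 2, 4, 8, 16, 24, 36 and 52 (8 collections), and the follow-up weeks are 54 and 60 (2 collections). Table 4 gives 0 screening, 8 main and 2 follow-up collections at 5 mL each: 10 × 5 = 50 mL. The two agree, so the blanks at Weeks 12 and 14 are not an extraction fault. Footnote N explains the absence of Group 2 samples up to Week 12. The Week 14 gap comes from the row itself.

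**2. Scheduled samples for Group 2.** Removing the footnote N samples leaves Weeks 16, 24, 36, 52, 54 and 60. The number before first dose is 0. From first dose (Day 84 or 98) to Week 16 (Day 112) is 28 or 14 days.

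**3. Apply SAP Section 10.** The classification, with post-dose positives lacking a baseline taken as inconclusive, was run over every combination of four titer levels (0, 10, 40, 160) at the six sampling times with no baseline, 4^6 = 4,096 patterns. The only results were negative and inconclusive. None was ADA-positive.

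**4. Effect on incidence.** Assume 9 and 3 subjects (the planned maxima), all dosed and evaluable.
- Group 2: 0/3 in every case.
- Overall maximum: 9/12 = 75%.
- Example with 3 of 9 positive in Group 1: overall is 3/12 = 25.0% however many Group 2 subjects respond. If 1 of 3 responded and could be counted, it would be 4/12 = 33.3%.

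**5. Expected dilution.** Let p1 and p2 be the true rates in Groups 1 and 2, and r = p2/p1.
- Reported overall = 9·p1/12.
- True overall = (9·p1 + 3·p2)/12.
- Ratio = 3/(3 + r).

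| r | Reported as a share of true |
|---|---|
| 1 | 0.75 |
| 0.5 | 0.86 |
| 0 | 1.00 |

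The documents give no ADA rate. For illustration only, with p1 = 20%:
- Reported overall is 9 × 0.20/12 = 15%.
- True overall is 20% at r = 1, and (9 × 0.20 + 3 × 0.10)/12 = 17.5% at r = 0.5.
- The chance that at least one of 3 Group 2 subjects responds is 1 − 0.8³ = 49% at r = 1, and 1 − 0.9³ = 27% at r = 0.5.

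**6. Precision for context.** Exact (Clopper-Pearson) 95% intervals are 2% to 48% for 2/12 and 3% to 60% for 2/9.

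**7. Which baseline would apply.** SAP 13.3 sets Group 2's baseline on or before randomization unless otherwise noted. SAP 13.5 takes the last repeated value before investigational product for safety parameters. Section 10 gives no ADA-specific rule. A sample newly drawn at Visit 7 or 8 would fall after randomization, so under 13.3 alone it would not count as baseline.

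**The case against.** The strongest reply is that SAP Section 10 anticipates this case. A post-dose positive without a baseline is named as inconclusive, and the same table shows positive, negative and inconclusive counts side by side. Sample-level counts, titers and listings would show it too. This stands: the information is not lost, and the defect is confined to derived percentages. It does not rescue those percentages, because the inconclusive subject remains in the incidence denominator.

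Other points that stand in part:
- **Sample counts.** Six post-dose samples in Group 2 against nine in Group 1 holds only for subjects who take the follow-up route. For Part B entrants the Part A counts are 4 and 7, and Part B adds samples in both groups. Less exposure and fewer samples in Part A make r below 1 plausible but do not establish it. The zero for Group 2 does not depend on r.
- **Baseline rule.** The tension between SAP 13.3 and 13.5 has little effect until a Visit 7 or 8 sample exists, and 13.5 may not extend to immunogenicity. It still has to be settled for the added sample to count.
- **Section 9.2.3.1.** It lists a predose PK sample and no ADA sample, but 9.2.1.2 also omits ADA for Group 1 on Day 1, where Table 1 schedules it. Silence in the visit lists proves nothing. The case rests on Table 1.
- **Materiality.** No hypothesis is tested, the SAP lists the endpoint as exploratory, and no primary, secondary or PK result changes.

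**Conclusion.** The concern holds and is minor. Followed exactly, the schedule and SAP Section 10 fix Group 2's ADA incidence at 0, and overall incidence is too low whenever a Group 2 subject truly responds. The Group 2 result does not depend on group size or on any assumed rate. The 75% ceiling and the dilution factors assume 9 and 3 subjects, all evaluable, and the 20% rate is illustrative. The Group 1 column, the inconclusive row, the sample-level counts, the neutralizing-antibody results and the listings are unaffected.

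This covers scheduled draws only. An unscheduled pre-dose sample, or a first dose delayed past the Week 16 draw, would change the position for that subject. The laboratory manual and the COVID-19 schedules (Protocol Tables 8 to 10) were not available.

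**What to change.** 1. **Protocol.** Add one pre-dose ADA sample for Group 2 at the existing blood draw at Visit 7 or 8, whichever precedes the first dose. Amend the Table 1 ADA row, footnote N and Table 4 to match.
2. **SAP Section 10, baseline.** Define the ADA baseline in both groups as the last sample before the first pegcetacoplan dose, overriding SAP 13.3 and 13.5 for this endpoint.
3. **SAP Section 10, subjects still without a baseline.** State that a post-dose positive is inconclusive and not negative. Leave all such subjects, positive or negative, out of the incidence denominator and show them on a separate line. Dropping only the positives would bias incidence downward. Amend the note equating incidence with the percentage ADA-positive so that both use the same denominator.

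**Cost.** A short protocol amendment, two or three SAP sentences, and one 5 mL tube and assay per Group 2 subject. The draw rises from 11 + 4 + 3 + 4 + 10 = 32 mL to 37 mL, within Table 4's 32 to 44 mL main-period range. If footnote N also removes Group 2's Week 12 PK tube, it rises from 28 to 33 mL. On the follow-up route, Group 2's total is now 653 − 20 (ADA) − 16 or 20 (PK) = 617 or 613 mL, and would become 622 or 618 mL, still below 653 mL.

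Step 1 cannot help Group 2 subjects already dosed. For them, steps 2 and 3 alone still prevent a misleading 0%, at the price of having no Group 2 incidence estimate.
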